8.2.2 Reactogenicity

Reactogenicity events are AEs that are known to occur with types of vaccine similar in composition to those being tested in this study. The following Toxicity Grading Scales will be used to grade solicited local (injection site) and systemic (subjective and quantitative) reactions:

Table 2: Assessment of Solicited or Expected Adverse Event Severity

Adverse Event	Grade	Severity
Pain/tenderness at injection site	1	Easily tolerated, does not interfere with activity
	2	Limits use of limb or interferes with daily activity
	3	Prevents daily activity
Erythema at injection site	1	< 10 mm
	2	10 mm – 25 mm
	3	> 25 mm
Induration/swelling at injection Site	1	< 10 mm
	2	10 mm – 25 mm
	3	> 25 mm
Fever (tympanic)	1	38.0°C – 38.4°C
	2	38.5°C – 38.9°C
	3	>39.0°C
Headache	1	Easily tolerated, does not interfere with daily activity
	2	Responds to non-narcotic pain reliever or interferes with daily activity
	3	Responds to narcotic pain reliever or prevents daily activity
Nausea	1	Easily tolerated, does not interfere with daily activity
	2	Decreased oral intake
	3	Minimal oral intake
Vomiting	1	1-2 episodes in 24 hours
	2	> 2 episodes in 24 hours
	3	Prevents daily activity or requires outpatient IV hydration
Myalgia	1	Easily tolerated, does not interfere with daily activity
	2	Interferes with daily activity
	3	Prevents daily activity
Arthralgia	1	Easily tolerated, does not interfere with activity
	2	Interferes with daily activity
	3	Prevents daily activity
Urticaria	1	Requiring no medications
	2	Requiring oral or topical treatment, or IV medication or steroids for <24 hours
	3	Requiring IV medication or steroids for >24 hours

Table 3: Assessment of Unsolicited Systemic Adverse Event Severity

Systemic AE	Mild (Grade 1)	Moderate (Grade 2)	Severe (Grade 3)
Anorexia	Decreased appetite without decreased oral intake lasting greater than 48 hours	Decreased appetite associated with decreased oral intake without significant weight loss	Loss of appetite associated with significant weight loss
Diarrhea	3 loose stools/24 hours	Liquid stools	Liquid stools > 4x the amount or number normal for this child
Constipation	Not Applicable	Hard, dry stools with a change in frequency	Resulting in abdominal pain
Fatigue	No interference w/activity	Some interference w/activity	Significant, prevents daily activity

Arthritis	Mild pain with inflammation, erythema or joint swelling – but not interfering with function	Moderate pain with inflammation, erythema or joint swelling – interfering with function, but not with activities of daily living	Severe pain with inflammation, erythema or joint swelling – and interfering with activities of daily living
Vasovagal episode (associated with a procedure of any kind)	Present without loss of consciousness	Present with transient loss of consciousness	Not Applicable
Cough	Transient-treatment no	Persistent cough; treatment responsive	Paroxysmal cough; uncontrolled with treatment
Bronchospasm, Acute	Transient; treatment; 70% - 80% FEV ₁ of peak flow	Requires treatment; normalizes with bronchodilator; FEV ₁ 50% - 70% (of peak flow)	No normalization with bronchodilator; FEV ₁ 25% - 50% of peak flow; or retractions present
Dyspnea	Dyspnea on exertion	Dyspnea with normal activity	Dyspnea at rest
Hypersensitivity	Transient flushing or pruritus without rash	Pruritic rash or mild urticaria	Symptomatic bronchospasm, with or without urticarial

Table 4: Assessment of Basic Body Function Adverse Event Severity

Vital Signs*	Mild (Grade 1)	Moderate (Grade 2)	Severe (Grade 3)
Tachycardia – beats per minute	115-130	131-150	>150
Bradycardia – beats per minute	55-59	50-54	<50
Hypertension** (systolic, mm Hg)	126-135	136-145	>145
Hypertension** (diastolic, mm Hg)	86-90	91-96	>96
Hypotension	Symptomatic, oral fluids not required	Symptomatic, corrected with oral fluid replacement	Symptomatic, IV fluids indicated

*Subject should be at rest for measurement of vital signs

**With repeat testing at same visit

Table 5: Assessment of Laboratory Adverse Event Severity

HEMATOLOGY	Grade 1 (Mild)	Grade 2 (Moderate)	Grade 3 (Severe)
Hemoglobin	8.2 – 9.2 g/dL	7.1 – 8.1 g/dL	<7.0 g/dL
Platelets	110,000 130,000/mm ³	– 90,000 109,999/mm ³	– <90,000/mm ³
WBCs (increase)	13,800 17,000/mm ³	– 17,001 20,000/mm ³	– <20,000/mm ³
WBCs (decrease)	2500 – 4200/mm ³	1500 – 2499/mm ³	<1500/mm ³
ANC (decrease)	750 – 1000/mm ³	500 – 749/mm ³	<500/mm ³
CLINICAL CHEMISTRIES	Grade 1	Grade 2	Grade 3
Serum creatinine	1.2 – 1.4 mg/dL	1.5 – 1.7 mg/dL	>1.8 mg/dL or requires dialysis
ALT	48 – 105 U/L	106 – 220 U/L	>220 U/L

All local (injection-site) reactions occurring within the first 14 days after vaccination will be considered definitely related to vaccination.

8.2.3 Serious Adverse Events

An SAE is an AE, whether considered related to a study vaccine or not, meeting one of the following conditions:

1. Death during the period of protocol-defined surveillance
2. Life threatening: defined as an event that places a subject at immediate risk of death at the time of the event and does not refer to an event that hypothetically might have caused death were it more severe
3. Hospitalization during the period of protocol-defined surveillance: defined as at least an overnight stay in the hospital or emergency ward for treatment that would have been inappropriate if administered in the outpatient setting
4. Results in a congenital anomaly or birth defect
5. Results in a persistent or significant disability or incapacity: defined as a substantial disruption of the study subject's ability to carry out normal life functions
6. Any other important medical event that may not result in death, be life threatening, or require hospitalization, may be considered a serious AE when, based upon appropriate medical judgment, the event may jeopardize the subject and may require medical or surgical intervention to prevent one of the outcomes listed above.

8.2.4 Procedures to be Followed in the Event of Abnormal Laboratory Test Values or Abnormal Clinical Findings

The Principal Investigator or appropriate co-investigator is responsible for reporting all AE/SAEs that are observed or reported during the study, regardless of the relationship to study products. AE/SAEs, abnormal clinical laboratory test values, or abnormal clinical findings will be documented, reported, and followed appropriately.

8.3 Reporting Procedures

8.3.1 Serious Adverse Events

All SAEs will be reviewed by a study physician, recorded on the appropriate SAE form, and followed through to resolution or stabilization by a study physician. All SAEs will be reported to AIGHD within 1 working day of notification of the SAE occurrence to the Principal Investigator, via either:

- Notification of the SAE via the eDM¹ system (automatic updates are then provided to all relevant pharmacovigilance staff), OR
- Notification via a scanned PDF version of an SAE form to [contact]. This distribution list will provide automatic distribution to all relevant pharmacovigilance staff.

In addition, the Principal Investigator will report all SAEs that are determined to be definitely or probably related to vaccination to the Institutional Review Board (IRB) that approved the study (i.e., the local IRB in Gabon) according to the IRB's reporting timelines and using the IRB-specified reporting forms, as well as to the Independent Medical Monitor.

All local and systemic reactions not meeting the criteria for SAE will be captured on the appropriate case report form (CRF). These events will be followed to resolution.

8.3.2 Regulatory Reporting

Following notification from the Principal Investigator, the IND sponsor (Sabin Vaccine Institute) will report events that are both serious and unexpected that are possibly, probably, or definitely related to the vaccine, to the FDA within the required timelines: fatal and life-threatening events within 7 calendar days (by phone, fax, or internet) and all other SAEs in writing within 15 calendar days. All SAEs not listed as possibly, probably, or definitely related will be reported to the FDA and ANVISA at least annually in a summary format.

All Adverse Events of Special Interest (AESIs; see below) will be reported to FDA according to the same procedure as for reporting SAEs, and according to the same timelines as described above.

¹ Electronic Data Management system

8.3.3 Adverse Events of Special Interest (AESI)

Special attention will be paid to monitoring for the occurrence of certain adverse events termed, “**Adverse Events of Special Interest**” or AESIs. These include inflammatory and autoimmune disorders that may potentially be related to the use of an immunostimulatory adjuvant (although none have been associated with the use of GLA-AF). The occurrence of the following AESI’s will be closely monitored:

- Neuroinflammatory disorders (optic neuritis, multiple sclerosis, demyelinating disease, transverse myelitis, Guillain-Barré syndrome, myasthenia gravis, encephalitis, neuritis, Bell’s palsy)
- Musculoskeletal disorders (systemic lupus erythematosus, cutaneous lupus, Sjogren’s syndrome, scleroderma, dermatomyositis, polymyositis, rheumatoid arthritis, juvenile rheumatoid arthritis, polymyalgia, rheumatica, reactive arthritis, psoriatic arthropathy, ankylosing spondylitis, spondylarthropathy)
- Gastrointestinal disorders (Crohn’s disease, ulcerative colitis, celiac disease)
- Metabolic diseases (autoimmune thyroiditis, Grave’s or Basedow’s disease, Hashimoto thyroiditis, insulin-dependent diabetes mellitus, Addison’s disease)
- Skin disorders (psoriasis, vitiligo, Raynaud’s phenomenon, erythema nodosum, autoimmune bullous skin diseases)
- Others (autoimmune hemolytic anemia, idiopathic thrombocytopenic purpura, antiphospholipid syndrome, temporal arteritis, Behcet’s syndrome, pernicious anemia, autoimmune hepatitis, primary biliary cirrhosis, primary sclerosing cholangitis, autoimmune glomerulonephritis, autoimmune uveitis, autoimmune cardiomyopathy, sarcoidosis, Stevens-Johnson syndrome).
- Vasculitides

8.3.4 Medically-Attended Adverse Events (MAAEs)

Special attention will also be paid to recording medically-attended adverse events, which are defined as any clinical symptom or diagnosis (including local symptoms at the injection site or systemic symptoms) for which medical evaluation and/or care is sought from a healthcare professional, outside of a regularly scheduled study visit. Note that MAAEs are not the same as SAEs. Whether or not an AE is an MAAE will be recorded on the appropriate Case Report Form.

8.4 Type and Duration of Follow-up of Subjects after Adverse Events

AEs will be recorded if they start from the time of the first study vaccination (Day 0) up to 28 days after each dose of study vaccine. AEs limited to new-onset chronic medical conditions will be followed through approximately 9 months after the third study vaccination (Day 380/448).

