2. To assess the distribution of IgG subclass responses to *Na-GST-1* and *Na-APR-1* (M74).

Exploratory:

1. To assess the cellular immune responses to the *Na-GST-1* and *Na-APR-1* (M74) antigens following immunization.
2. To assess the impact of co-administered *Na-GST-1* and *Na-APR-1* (M74) on the production of memory B cells specific for each antigen.
3. To assess the production of memory B cells specific for each vaccine antigen compared to metabolomic changes before and after vaccination
4. To characterize the metabolite composition in urine and serum during the course of immunization and assess the changes on metabolite profiles related to the co-administration of *Na-GST-1* and *Na-APR-1* (M74).

Description of Study Design:

Double blind, randomized, controlled, dose-escalation Phase 1 clinical trial in hookworm-exposed children aged 6 to 10 years living in the area of Lambaréne, Gabon. Children will receive three doses of the assigned vaccine(s) delivered intramuscularly (deltoid) on approximately Days 0, 56, and 112 or 180.

Safety will be measured from the time of each study vaccination (Day 0) through 14 days after each study vaccination by the occurrence of solicited injection site and systemic reactogenicity events.

Unsolicited non-serious adverse events (AEs) will be collected from the time of the first study vaccination through approximately 1 month after each study vaccination. New-onset chronic medical conditions and Serious Adverse Events (SAEs) will be collected from the time of the first study vaccination through approximately 9 months after the third study vaccination (final visit). Clinical laboratory evaluations for safety will be performed on venous blood collected approximately 14 days after each vaccination.

Immunogenicity testing will include IgG antibody responses to each vaccine antigen, by a qualified indirect enzyme-linked immunosorbent assay (ELISA), on serum or plasma obtained prior to each study vaccination and at time points after each vaccination (see Appendix A); the functional activity of vaccine-induced antibodies will be assessed by *in vitro* enzyme neutralization assays; the induction of B cell memory will be measured by antigen-specific memory B cell responses.

Recruitment and enrollment into the study will occur on an ongoing basis, with each group being recruited and vaccinated in sequence.

60 subjects will be enrolled into 3 groups of 20:

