2.2 Study Outcome Measures

2.2.1 Primary Outcome Measures

Safety

The following parameters will be evaluated for each dose of *Na-APR-1* (M74) co-administered with *Na-GST-1*:

1. Frequency of solicited injection site and systemic reactogenicity, graded by severity, on the day of each study vaccination through 14 days after each study vaccination.
2. Frequency of study vaccine-related serious adverse events from the time of the first study vaccination through approximately 9 months after the last study vaccination.
3. Frequency of clinical safety laboratory adverse events.
4. Frequency of unsolicited adverse events, graded by severity, from the time of each study vaccination through approximately 1 month after each study vaccination.
5. Frequency of new-onset chronic medical conditions through approximately 9 months after the third study vaccination.
6. Frequency of Adverse Events of Special Interest through approximately 9 months after the third study vaccination.

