6.5 Early Termination Visit

The following activities will be performed at the early termination visit for study participants who withdraw, or are withdrawn or terminated from the study:

- Obtain interim medical history by interview of subjects and note any changes since the previous visit.

- All concomitant medications will be recorded on the appropriate data collection form (if within 28 days of child's last vaccination received in the study).
- Information regarding adverse events/Serious Adverse Events will be assessed and recorded on the appropriate data collection form (adverse events will be limited to new-onset chronic medical conditions and SAEs if after 28 days after the third study vaccination).
- A targeted physical examination may be, if indicated based on review of interim medical history.
- Approximately 2.4 mL of venous blood may be collected for safety labs and performed by the clinical laboratory (if prior to the post-vaccination day 14 visit and if not recently obtained per study schedule).
- Approximately 6.2 mL of venous blood may be collected for antibody and cellular assays (if prior to post-vaccination day 14 visit and if not recently obtained).

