6.6 Unscheduled Visit

Unscheduled visits may occur at any time during the study. Any of the following activities may be performed:

- Review concomitant medications (if started prior to 28 days after a study vaccination).
- Review adverse events (if started prior to 28 days after a study vaccination).
- Review serious adverse events and new-onset chronic medical conditions
- Obtain medical history by interview of children and their parent/guardian and note any changes since the previous visit (if indicated).
- A targeted physical examination may be performed, if indicated based on review of medical history.
- Examine study vaccination site (if within 14 days after a study vaccination).
- Approximately 2.4 mL of venous blood will be collected for safety labs and performed by the study clinical laboratory (if indicated).

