8.5 Halting Rules

If a dose of study vaccine is considered significantly reactogenic (see below and Section 8.6.2), dose escalation and/or additional vaccinations will be suspended until reviewed by the SMC, Independent Medical Monitor, and IND sponsor (SVI). Any recommendation of the Independent Safety Monitor and/or SMC to resume or suspend further injections (either for an individual subject, an entire Group, or the full study) will be communicated in writing to the sponsor and Principal Investigator. All communications from the SMC will subsequently be forwarded by the investigators to the IRB.

The following criteria will be used to define significant reactogenicity:

- One or more participants experience a protocol defined SAE that is determined to be possibly, probably, or definitely related to a study vaccine, **OR**,
- One or more participants experience a protocol defined AESI that is determined to be possibly, probably, or definitely related to a study vaccine, **OR**,
- One or more participants experience a protocol defined Grade 3 hypersensitivity reaction that is possibly, probably or definitely related to a study vaccine, **OR**,
- Two or more participants experience a protocol defined Grade 2 hypersensitivity reaction that is probably or definitely related to a study vaccine, **OR**,
- Three or more participants in a single Group (i.e., Group 1, Group 2, etc.) experience the same objective physical finding or laboratory abnormality of Grade 3 or higher (with the exception of isolated Grade 3 erythema or swelling), that is determined to be probably or definitely related to a study vaccine, **OR**,
- Three or more participants in a single Group experience the same Grade 2 or higher safety laboratory abnormality or Grade 3 clinical AE that is possibly, probably or definitely related to a study vaccine.

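### The late event-collection wording in 8.4, 6.5, 6.6 and the synopsis does not name Adverse Events of Special Interest, although AESIs to about 9 months after dose 3 are a primary outcome

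*Combined protocol and SAP*

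**What the plan says.** Section 2.2.1 lists as primary outcome 6: "Frequency of Adverse Events of Special Interest through approximately 9 months after the third study vaccination". Section 10.3 repeats it. Section 8.1 (item 6) sets the same period, from first vaccination to about 9 months after the last. Appendices A1 and A2 have a combined AE/SAE/AESI assessment row that runs well past the 28-day windows. One of the suspension criteria in 8.5 begins "One or more participants experience a protocol defined AESI" and requires that the event be at least possibly related to a study vaccine.

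Four other places say what is recorded in the late period:

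- **Section 8.4** records adverse events that start up to 28 days after each dose, and then: "AEs limited to new-onset chronic medical conditions will be followed through approximately 9 months after the third study vaccination (Day 380/448".
- **Section 6.5**, for the early termination visit: "adverse events will be limited to new-onset chronic medical conditions and SAEs if after 28 days after the third study vaccination".
- **Section 6.6**, for unscheduled visits, covers adverse events that began before 28 days after a vaccination and adds, without a time limit: "Review serious adverse events and new-onset chronic medical conditions".
- **The synopsis** collects non-serious unsolicited events to about a month past each dose. Its list for the longer period, which runs to the final visit, is: "New-onset chronic medical conditions and Serious Adverse Events (SAEs) will be collected from the time of the first study vaccination through approximately 9 months".

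None of the four names AESIs.

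**The concern.** A primary outcome can be no more complete than the rule that tells staff what to write down. Sections 2.2.1 and 8.1 treat SAEs, new-onset chronic conditions and AESIs as three separate items, so a rule that names one or two of them does not cover the third. The AESI list in 8.3.3 includes conditions such as Bell's palsy, neuritis, reactive arthritis and erythema nodosum. A case that resolves and meets none of the SAE conditions in 8.2.3 is neither serious nor chronic, and it falls outside the late wording.

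The AESI outcome is aimed at possible effects of the immunostimulatory adjuvant, in 60 children. One event can change the count from zero to one, and one related event can suspend vaccination. A rule that lets even a few such events go unrecorded or be recorded late therefore matters more than its length in the text suggests.

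**Working it through.** **1. The passages side by side, for an event that starts outside the 28-day windows**

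| Place | What it covers | AESIs named? |
|---|---|---|
| 2.2.1, 8.1, 10.3 | AESIs to about 9 months after the last dose | Yes |
| Appendix A1/A2 | AE/SAE/AESI assessment at scheduled visits | Yes |
| 8.4 | New-onset chronic conditions only | No (nor SAEs) |
| 6.5 | Chronic conditions and SAEs, if more than 28 days after dose 3 | No |
| 6.6 | SAEs and chronic conditions | No |
| Synopsis | Chronic conditions and SAEs | No |

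The four late rules are not alike. Section 8.4 omits SAEs as well. Section 6.5 is the only visit rule that expressly limits, and only after dose 3. Section 6.6 lists what may be done. The synopsis is a list of what is collected.

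**2. Where the 6.5 limit applies.** Dose 3 is on Day 112 or 180 and follow-up ends on Day 380 or 448.

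- 0,2,4 schedule: 112 + 28 = Day 140, and 380 − 140 = 240 days.
- 0,2,6 schedule: 180 + 28 = Day 208, and 448 − 208 = 240 days.

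These are the days on which an early termination would fall under the limit. They are not days without AESI collection.

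**3. What scheduled visits recover.** After those dates the visits are Days 200, 290 and 380, or Days 268, 358 and 448.

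- Intervals on 0,2,4: 200 − 140 = 60; 290 − 200 = 90; 380 − 290 = 90.
- Intervals on 0,2,6: 268 − 208 = 60; 358 − 268 = 90; 448 − 358 = 90.

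For a child who attended every visit until then, the events at risk of omission at early termination are those since the last scheduled visit, nominally at most 90 days. No later scheduled visit exists to pick them up. Neither appendix has a column for early termination or unscheduled visits, so the assessment row does not settle 6.5 or 6.6.

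**4. Children seen unscheduled who stay in the study.** The next scheduled visit asks again, so the effect is delay. The longest nominal interval between visits is on the 0,2,6 schedule: 180 − 84 = 96 days. Appendix A2 marks the AESI assessment at Day 180, and section 6.3 lists history and examination there before the vaccine is given.

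**5. Bearing on the suspension criterion.** It acts only while doses remain to be given. Under 4.3.2 the first 10 children in each Group follow 0,2,4 and the last 10 follow 0,2,6. A 0,2,4 child passes Day 140 at least 180 − 140 = 40 nominal days before the 0,2,6 children of the same Group are due dose 3. An event in an early terminator can therefore still bear on remaining vaccinations.

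**6. The plan's own detection figure.** Section 10.1 gives 83.92% for at least one event with N=60 at a true rate of 3%: 1 − (1 − 0.03)^60 = 0.8392, which reproduces. That figure presumes that every event is recorded. The documents do not say what share of AESIs would be non-serious and resolving, or how many children terminate early, so no adjusted figure follows.

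**The case against.** The strongest reply is that the protocol as a whole does collect late AESIs. Section 8.1 sets the period, the Appendix A row schedules the assessment, 8.3.3 calls for close monitoring and 8.3.2 gives AESIs the same FDA route and timelines as SAEs. Sections 7.1 and 8.2.1 require an adverse event reported to a study clinician to be documented in full, with no 28-day limit, and 8.2.4 makes the investigator responsible for reporting everything observed or reported during the study. Section 6.6 is permissive, and both 6.5 and 6.6 include an interim history. Section 8.4, read as exhaustive, would also lose late SAEs, which 8.1 plainly includes, so it is better read as incomplete shorthand. Many listed AESIs are chronic diseases, and the important-medical-event condition in 8.2.3 can bring in others as SAEs.

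Most of this stands, and it rules out several stronger readings:

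- A reader might infer that AESIs are not collected outside the 28-day windows, and count 381 − 87 = 294 of 381 calendar days on one schedule and 449 − 87 = 362 of 449 on the other (three windows of 29 days each) as uncovered. Those are days outside the general adverse-event window; scheduled visits in that time assess AESIs.
- A reader might infer that children who withdraw or come in unscheduled are the likeliest to have an AESI. The documents give no support for that.
- A reader might infer that the suspension criterion is bypassed. It needs at least possible relatedness, and the 0,2,6 child is assessed on Day 180 before dose 3.

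The reply does not remove the conflict. Section 6.5 says in terms that late events at early termination are limited to two types, and that specific instruction contradicts 8.1 and the general duty in 8.2.4. Staff should not have to choose between them.

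**Conclusion.** The concern holds as an internal inconsistency with a narrow consequence. The primary outcome, the safety parameter and the assessment schedule include AESIs to about 9 months after dose 3; the late wording in 8.4, 6.5, 6.6 and the synopsis does not name them. Read literally, a non-serious AESI that resolves can be left out for a child who terminates early more than 28 days after dose 3, and can be picked up late for a child seen unscheduled between visits.

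This rests on two assumptions: that staff follow the visit-specific wording rather than the general duty to report, and that the event meets no SAE condition and does not become chronic. The number of children or events affected cannot be derived from the documents. The text should be reconciled because the outcome is primary, a single case counts, and the correction is cheap.

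**What to change.** Reconcile the passages. In 8.4, 6.5, 6.6 and the synopsis, state the late scope in the same words: *SAEs, AESIs and new-onset chronic medical conditions, from first vaccination to Day 380/448*. In 8.4 this also restores the missing SAEs. Have the early-termination and unscheduled-visit forms ask about AESIs whatever the time since the last dose.

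The cost is wording in four places and one CRF item. No visit, procedure, sample size or stated probability changes, and the suspension criteria in 8.5 stay as written.
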